5. STUDY EVALUATIONS AND MEASUREMENTS

List variables that will be abstracted from medical charts: none

Describe screening evaluation: Vital signs, including heart rate, respiratory rate, temperature and blood pressure will be collected. Oxygen saturation levels will be noted, as well as breath sounds. A brief physical examination, including but not limited to the cervical lymph nodes, eyes, ears, nose, throat, cardiovascular and respiratory systems.

Describe how measurements will be taken:

Covid:

All University, National and State guidelines will be followed during the Covid 19 pandemic, and the protocol will make changes as required to be in compliance. There will only be 1 subject at any given time in the study area, and areas will be cleaned between subjects. As many of the procedures for this study are considered to be aerosol generating, all subjects will be verbally screened for signs or symptoms of Covid, or recent potential exposure. Staff will be encouraged to receive vaccination. Study participants will be masked when it does not interfere with measurements. Study staff will wear appropriate PPE during visits. Spirometry and aerosol treatments will be done in rooms with either > 6 air exchanges per hour or with running HEPA filters. Any subject will be deferred for at least 90 days after a positive Covid test, and volunteers will be required to show proof of up to date vaccination.

Spirometry:

This test measures the volume of air that can be exhaled and the rate of airflow during exhalation after a maximal inhalation, and is performed to American Thoracic Society (ATS) guidelines. Subjects will inhale as deeply as possible, then exhale as rapidly and completely as possible into the spirometer. Measurements obtained from each maneuver include the forced vital capacity (FVC), the forced expiratory volume in the first second (FEV1), the maximal mid-expiratory flow rate (FEF 25-75%) and the peak expiratory flow (PEF). The largest FVC and FEV1, from at least 3 acceptable trials, are selected for analysis; the flow rates are selected from the trial with the largest sum of FVC and FEV1.

FeNO:

Fractional Exhaled nitric oxide (FeNO) is measured using the Niox MINO (Aerocrine Inc) device. The subject inhales through the mouth to total lung capacity (TLC) and then exhales immediately. The NO analyzer samples the expirate continuously. Since exhaled NO plateau values can vary with exhalation flow rate, subjects must achieve a standardized expiratory flow rate for the results to be acceptable. eNO is measured in parts per billion (ppb). The procedure is performed in accordance with ATS guidelines.

HS Inhalation:

The subject will be instructed on the proper use of the PARI LC Star Nebulizer System, an approved device for aerosol inhalation. The subject will use the nebulizer until the HS dose is completed. All subjects in this study will be pretreated with albuterol prior to HS inhalation.

MCC procedures:

Prior to each MCC study, a transmission Co57 scan will be performed to define the lung boundaries, to assign regions of interest, and to normalize these regions for lung volume differences (**Fig 2**). A rectangular phantom containing the radioisotope Co57 (< 25 mCi) will be placed in front (5cm) of the subject sitting with his/her back to the gamma camera for 30 seconds. The transmission scan has been used by us (e.g. 05-2358, 08-0795, 06-1016, 13-1605, 15-938) and others to provide a delineation of lung boundaries for assessing regional deposition/clearance of the inhaled radioaerosol. Prior to the transmission scan on each study day we will place 2 spot markers of Americium241 (0.9 microcurie (uCi) each, gamma 66 KeV) on the upper and lower back of each subject during scanning (both Tc99m-SC deposition/retention and Co57 transmission). With dual isotope imaging, these spot markers will allow alignment of images for more accurate determination of regional deposition/retention. These very low radiation sources have been obtained from commercially available home smoke alarms. The placement of these markers will be determined to be outside the lung field during the transmission scan. Their location

will be marked in semi-permanent ink for later placement during Tc99m deposition/retention scans. The shielded side of this source will be placed/taped onto the subject's skin.

Radiolabeled Tc99m-sulfur colloid will be delivered using a modified Pari-LL nebulizer (MMAD 9.5 um). This is a closed delivery system that produces 80 ml/sec air flow, and therefore limits the inspiratory flow rate to this value. While seated in front of a gamma camera subjects will perform single inhalations lasting ~10 seconds each from the delivery system, and will exhale at 500 ml/sec (using feedback from a flow meter in the breathing circuit). Approximately 5 of these inhalation maneuvers will be required to deposit an adequate isotope dose to the lung. Subjects will be allowed to breathe normally (off the nebulizer) in between each inspiratory maneuver. Each volunteer will practice these maneuvers prior to the actual radioaerosol inhalation to guarantee his/her proficiency. The activity of Tc99m-SC loaded in the nebulizer will be adjusted to provide an estimated 40 uCi deposited in the lung for each MCC scan. A single crystal detector will be placed at the subject's back during inhalation to monitor dose to the lung. Total inhalation time should be less than 5 minutes in all cases. Immediately following isotope inhalation, the subject will gargle and drink water to clear activity that deposited in the mouth into the stomach. The subject will then (within a minute of final inhalation maneuver) be seated in front of a large-field-of-view gamma camera to begin acquiring particle retention images.

For the baseline MCC measurement, the gamma image capture will begin immediately and will capture continuously for the first 34 minutes. Thereafter, 2 consecutive 2-minute images will be obtained at the start of every 10-minute period until 2 hours have passed. For visit 3/5, participants will first inhale Tc99m-SC as described above then sit in front of the gamma camera for 4 minutes during which images of the lung will be continuously captured. While still sitting in front of the gamma camera, they will inhale HS. Image capture will be continuous during HS inhalation and for the next 34 minutes, after which 2 consecutive 2-minute images will be obtained at the start of every 10-minute period until 2 hours have passed. The subject will also return the day (visit 4/6) following each MCC measurement to sit in front of the gamma camera for 30 minutes to obtain images of the lungs to visualize retention of Tc99m-SC particles. No Tc99m-SC will be administered at this visit. Spirometry, symptom questionnaire, and vital signs will be collected prior to discharge on the follow up day.

Hypertonic Saline Induced Sputum procedure:

Prior to sputum induction, subjects will have spirometry measured for FEV1 and FVC values. Next, an ultrasonic nebulizer filled with 20 cc of 3% hypertonic saline (inhalation grade for respiratory use only, 3% NaCl) will be set to the maximum output setting and turned on. The subject will be instructed to latch his/her mouth onto the nebulizer mouthpiece and breathe normally (i.e., tidal breaths) for 7 minutes as the saline is nebulized through the mouthpiece in a jet stream and inhaled. The nose will not be occluded for this procedure. The subject will be encouraged to come off the mouthpiece at any time to cough if a sputum sample from the lower

[figure not shown]

Figure 2. (A) Initial deposition of radiolabeled particles (top) and 20 minutes later (bottom) in the lungs of an asthmatic subject detected with gamma scintigraphy.

(B) MCC expressed as retention of labeled particles vs time. In our prior study of gamma tocopherol (Vitamin E) vs placebo, LPS challenge reduced MCC during placebo (squares) but not during active treatment (diamonds).

airways (i.e. not from the back of the throat) is ready for expectoration. Prior to expectoration, subjects will be asked to blow their nose, rinse their mouth with water, and clear their throat to avoid the inclusion of non airway fluid samples. The sample will be expectorated into a sterile specimen jar and capped.

Following the measurement of FEV1 after the first 7 minute inhalation period, the concentration of saline will be increased from 3% to 4%, provided the FEV1 decrement is < 10% from the post bronchodilator value. If the FEV1 falls between 10-20% of the post bronchodilator value, the test will proceed but the concentration of saline will remain the same. If the FEV1 falls by > 20% or if troublesome symptoms occur, the nebulization will be discontinued, and albuterol will be immediately available if necessary to relieve symptoms. The same procedure will be followed for the final 7 minute inhalation period using 5% hypertonic saline provided the FEV1 safety parameters described above have been met. The nebulization is stopped after a total of 21 minutes or earlier if a sputum sample of good quality is obtained (i.e. visible sputum plugs). Subjects may request early termination at any time the procedure becomes intolerable.

5.1 Efficacy Evaluation (if applicable)

To determine the efficacy of HS for accelerating MCC associated with 3% vs. 7% HS treatment as compared to baseline MCC in adult patients with moderate to severe asthma. MCC is measured as the average % retention of radiolabeled particles in the lung over a 120 minute measurement period.

5.2 Pharmacokinetic Evaluation (if applicable)

None

5.3 Safety Evaluations: The primary safety criteria will be change in FEV1 from baseline measures obtained on the same day. A drop in FEV1 by 10% at the 30-minute mark after HS inhalation will be considered an adverse event for patient safety and will result in withdrawal of the subject from further participation in the study.

During visit 1, subjects will be monitored for 1 hour after HS inhalation. If a subject's FEV1 is reduced by $\geq 10\%$ from that day's baseline at the 5-minute mark, spirometry will be repeated every 5 minutes up to 30 minutes. If at the 30-minute mark FEV1 is still reduced by $\geq 10\%$, 4 puffs of albuterol will be administered. Albuterol 4 puffs with spacer will be repeated if the participant has symptoms, or if FEV1 does not spontaneously return to within 5% of baseline values at the 1-hour mark.

Oxygen saturation will be monitored during the HS inhalation through the rest of the day's study procedures. Several studies have shown that the oxygen saturation drops transiently in patients with CF and COPD when they inhale a mucolytic agent. It is anticipated that asthmatic subjects will have a similar response.

Vital signs are monitored, including HR, RR, and BP. Auscultation is performed to determine if wheezing is present.

We will assess symptoms at baseline, prior to HS, and following HS whenever vital signs are measured. We will use the following symptom score questionnaire:

Symptom score (scale 0-none, 1-mild, 2-moderate, 3-severe):

Malaise____, Fatigue____, Shortness of Breath____, Cough____, Myalgia____,
Chills____, Fever____, Headache_____

Mild: Symptom minimally noticeable but would not ordinarily cause you to stop normal activities such as going to work or school and would not keep you from undertaking physical exercise.

Moderate: Symptom present but would not ordinarily cause you to stop normal activities such as going to work or school, although it might stop you from doing physical exercise ("working out")

Severe: Symptom clearly present and would cause you to consider not going to work or school or seek medical attention (such as calling a health care provider, going to student health, going to the emergency room, or taking medications for these symptoms).

HS treatment will be deferred if baseline total symptom score > 2, OR any shortness of breath or fever are reported, OR if any symptom rated as moderate (2) or severe (3). For symptom scores obtained after HS treatment, subjects will be assessed by a study physician if total symptom score >2, if ANY shortness of breath is reported, or if any symptom is rated as moderate (2) or severe (3). If following HS treatment, the participant ranks any symptom as severe (3), that participant will be excluded from further study.

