3.1 Study Design

Type of design: Prospective open label study

Provide brief overview of the study phases:

- **Visit 1 Baseline MCC:** Participants will inhale Tc99m-SC, assessment of MCC over a 2-hour period to define baseline MCC. Participants will then perform spirometry, followed by sputum induction.
- **Visit 2 Follow-up Baseline Visit:** Participants will return the following morning for a query of symptoms overnight. Spirometry will be performed. Participants will sit in front of the gamma camera for 30 minutes to estimate retention of Tc99m-SC in the airways.
- **Visit 3 Albuterol Treatment visit:** Between 1-6 weeks of the baseline visit, participants will return to the lab to complete spirometry and the symptom questionnaire. They will then inhale Tc99m-SC and immediately be scanned by gamma scintigraphy to measure deposition of the radiolabeled particles in the airways (4 minute scan). While they remain seated in front of the gamma camera they will then inhale 4 puffs of albuterol. MCC measurement will be performed for a 2-hour period post-radioaerosol inhalation to measure acute effects of albuterol on MCC. Subjects will undergo sputum induction at the completion of the MCC scan.
- **Visit 4 Follow-up Albuterol Treatment Visit:** Participants will return the following morning for a query of symptoms overnight. Spirometry will be performed. Participants will sit in front of the gamma camera for 30 minutes to estimate retention of Tc99m-SC in the airways.
- **Visit 5: 7% HS concentration comparison:** Participants will return to the lab
- Between 1-6 weeks of the albuterol visit, participants will return to the lab to complete spirometry and the symptom questionnaire. They will then inhale Tc99m-SC and immediately be scanned by gamma scintigraphy to measure deposition of the radiolabeled particles in the airways (4 minute scan). While they remain seated in front of the gamma camera they will then inhale 4 puffs of albuterol followed by 4 mL of nebulized 7% HS. MCC measurement will be performed for a 2-hour period post-radioaerosol inhalation (which includes the period of HS inhalation) to measure acute effects of HS on MCC. Subjects will undergo sputum induction at the completion of the MCC scan.

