3. Heart rate, blood pressure, or respiratory rate increase of more than 30% from baseline values (established on the same day).
4. Oxygen saturation < 90% for > 1 hour.
5. ANY reported shortness of breath, and any symptom ranked as severe (“3”).
6. Requirement of oral corticosteroid treatment for exacerbation of asthma associated with the HS inhalation.

Safety criteria for initiating suspension of further study until consultation with the DSMB and IRB will include the following:

1. The occurrence of any Serious Adverse Event.
2. If 3 of the first 10 participants fail the individual safety criteria outlined above.

Subjects will be under direct supervision of a study physician throughout the HS inhalation and MCC measurement, and will have contact information for after-hours access to a study physician. An asthma action plan with emergency medications will be provided to each subject after the HS visits in the event of an unexpected event, such as wheezing or bronchospasm overnight.

4.12 Screen failure procedures. For subjects who do not meet enrollment criteria, all study related activity will stop once it is determined that the subject does not meet criteria.

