6.2 Secondary Endpoints

a. change in MCC from baseline immediately after albuterol inhalation. This endpoint is of exploratory interest.

b. Safety measures for HS treatment in moderate to severe asthmatics will include change in the following from baseline:

- Vital signs (HR, RR, BP and oxygen saturation)
- Spirometry (FEV1, FVC)
- Symptom Questionnaires
- Physical exam (wheezing on chest auscultation, for example)

We will also assess:

- Adverse events and Serious Adverse events
- Proportion of participants who are deemed 'intolerant' to HS (i.e. those who experience a persistent reduction in FEV1 of $\geq 10\%$ from that day's baseline at 30 minutes post-HS, those who report shortness of breath, those who report a score of "3" for any individual symptom criterion, or those who experience oxygen saturation levels below 90% for > 1 hour).

Safety endpoints will be assessed continuously during the study period for monitoring of adverse events and individual stopping criteria. All adverse events whether or not listed in the NCI-CTCAE (see Section 9) or whether they are or are not related to study participation will be graded on a scale from 1 to 5 according to the standards in the NCI-CTCAE manual. Adverse events will be reported to the UNC IRB, the UNC DSMB, and the NHLBI project officer. The DSMB will review the protocol after 5 subjects have completed study procedures or at 6 months after enrollment begins, whichever is soonest, and then every 6 months thereafter.

Exploratory endpoints will also be assessed. These will focus on sputum cellularity, mediators in sputum (e.g. T1 cytokines: IL-1 β , IL-6, IL-8, TNF α , T2 cytokines, IL-4, IL-5, IL-13), eicosanoids,

and mucins (total mucins, MUC5AC, MUC5B).

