- **Adverse Event/Serious Adverse Event reporting procedures:** AE's and UP's will be reported to the IRB. The IRB, DSMB, and funding agency will be notified of any SAEs. The DSMB will review progress after the first 5 participants have completed the protocol or at 6 months after enrollment begins, whichever is soonest, and then every 6 months thereafter.
- **Medical Emergency procedures:** There is a study physician available for all inhalation procedures. A code cart and Automated External Defibrillator (AED) are available in the event of a cardiopulmonary event. Albuterol, both inhalers and nebulizers, are available in the event of bronchospasm. If a subject has an event that does not immediately respond to care in the research lab, he/she will be transported via EMS to UNC Healthcare for treatment.
- **Data Safety Monitoring Plan:** Data is initially recorded on paper documents, and the documents are maintained in a binder which is kept in a locked office within the EPA Human Studies facility. The EPA HSF is a secure facility with a guarded entrance and requires identification for entry. This data is then entered into REDCap by an initial data entry person, and confirmed by a second user.

- **Potential Risks:**

Potential Risks of Hypertonic Saline Inhalation:

Inhalation of hypertonic saline carries a small risk of bronchospasm, which may lead to the onset of asthma symptoms.

Potential Risks of Spirometry:

Potential risks include possible lightheadedness or wheezing.

Potential Risks of Mucociliary clearance scan:

The radiation risks for the MCC scan, including the Cobalt 57 transmission scan and the Americium 241 disks, which are used as fiducial markers is approximately 133 mRems. Adults in the New York City area receive about 300mRems per year in natural radiation exposure.

Potential Risks of Sputum Induction:

- Sputum induction may induce cough, chest tightness or bronchospasm **Protections Against Risk:**

Protections to Minimize Risk of Hypertonic Saline Inhalation:

A CEMALB physician is present in the building at all times during HS inhalation. All asthmatic subjects are pretreated with albuterol inhalation prior to hypertonic saline administration. Additional albuterol will be given after HS inhalation if FEV declines by $\geq 10\%$ from that day's baseline at the 30 minute spirometry measurement, if the participant develops symptoms of an asthma attack such as wheezing, or if the participant requests albuterol treatment.

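### The symptom questionnaire has no item for chest tightness or patient-reported wheeze, and the section 6.2 intolerance definition leaves out wheeze

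*Combined protocol and SAP*

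**What the plan says.** Section 5.3 of the combined protocol and SAP presents the instrument with the words "We will use the following symptom score questionnaire". Each item is scored 0 to 3. The items are "Malaise____, Fatigue____, Shortness of Breath____, Cough____, Myalgia" and "Chills____, Fever____, Headache".

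The answers are used in several places. Later in section 5.3 they drive deferral of HS, assessment by a study physician, and exclusion from further study. In section 6.2 the questionnaire is a safety measure. It also supplies two limbs of the intolerance definition: any reported shortness of breath, and a score of 3 "for any individual symptom criterion".

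On expected reactions, section 9 says of the study treatment: "Inhalation of hypertonic saline carries a small risk of bronchospasm, which may lead to the onset of asthma symptoms". Of the other saline exposure it says: "Sputum induction may induce cough, chest tightness or bronchospasm". Section 4.11 provides an action plan and emergency medication after HS visits for events "such as wheezing or bronchospasm overnight". For the day after each scan, section 3.1 states: "Participants will return the following morning for a query of symptoms overnight".

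**The concern.** Safety of HS in moderate to severe asthma is a secondary objective, and the synopsis names symptom scores as one of the ways to measure it. Six of the eight items are general symptoms of the kind seen with a febrile illness. Two typical complaints of airway narrowing, tightness and wheeze, have no line on the form, although the protocol anticipates both after saline.

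A symptom without a line cannot be scored 3. It therefore cannot meet the severe-symptom limb of intolerance, and it cannot appear in the symptom summary. If such events occur alone, the reported tolerability of HS will look somewhat better than it was. The reader of the results could not tell, because nothing was recorded.

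**Working it through.** The plan gives no figure to reproduce. The check is a match of the listed items against the reactions the protocol anticipates and against the rules that use the score.

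**Item count (section 5.3).** Eight items: two respiratory (shortness of breath, cough) and 8 − 2 = 6 general. None covers chest tightness and none covers wheeze.

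**Anticipated reactions against capture.**

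| Reaction | Where anticipated | Scored item | Other capture |
|---|---|---|---|
| Cough | Section 9, sputum induction | Yes | AE review |
| Shortness of breath | Rules in 5.3 and 6.2 | Yes; any report meets 6.2 | AE review |
| Bronchospasm | Section 9 (HS and induction); 4.11 overnight | Not itself a symptom item | FEV1, with spirometry at every visit |
| Wheeze | 4.11, overnight after HS visits | No | Auscultation; physical exam at Visits 1, 3 and 5 only (procedures table) |
| Chest tightness | Section 9, sputum induction only | No | None by name |

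**Three cases traced through the rules.**

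1. *Wheeze heard on the treatment day.* It is recorded as a safety measure (6.2), counts as intolerance under section 4.1, and suspends participation under 4.11 if it continues. The section 6.2 intolerance definition lists FEV1, shortness of breath, a score of 3 and oxygen saturation, but not wheeze. So wheeze alone counts as intolerance in 4.1 and does not in 6.2.

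2. *Isolated tightness on the treatment day.* Suppose there is no shortness of breath, no other item at 3, no qualifying FEV1 fall and no sustained desaturation. No item records the tightness and no limb of 6.2 is met.

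3. *Tightness or wheeze overnight, self-treated and gone by morning.* Every subject goes home with an albuterol inhaler (4.9). The section 5.3 description of severe includes taking medication for the symptom, so this event could fit a score of 3, but there is no line to score. At the follow-up visit, sections 4.2, 4.4 and 4.6 list vital signs, the same questionnaire, imaging, FeNO and spirometry, and the procedures table has no physical exam. Spirometry may by then be normal. Under section 9 an adverse event needs a failed safety criterion, a qualifying fall in lung function, or symptoms that lead to medical attention from a provider. Self-treated symptoms at home need not meet any of these.

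**Direction and unit size.** The 6.2 definition is a list of alternatives, so a symptom that cannot be scored can leave the count of intolerant subjects unchanged or lower it, never raise it. Section 6.3 reports the proportion among enrolled patients, planned as 28 (3.3 and 6.4). One missed case is 1/28 = 0.0357, or 3.6 percentage points. The 21 in section 6.4 is the number needed for power. If one assumes that 21 are exposed to HS and uses them as the denominator, one case is 1/21 = 0.0476, or 4.8 points. Neither figure says how many cases would be missed.

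**The case against.** The strongest reply is that the questionnaire is not the main detector of airway narrowing. Section 5.3 makes same-day change in FEV1 the primary safety criterion, and a fall of at least 10% at 30 minutes is intolerance under 6.2. Spirometry is scheduled at every visit. Any report of shortness of breath is enough for intolerance. Wheeze is treated as an examined sign, with its own place in 4.1, 4.11 and 6.2. After discharge there is a query about overnight symptoms, and review of adverse events is marked at every visit.

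All of this stands, and it rules out several stronger readings. A reader might infer that the reactions expected from saline cannot be scored; cough can be, and so can shortness of breath. A reader might infer that the safety assessment as a whole is blind to bronchospasm; FEV1 answers that. A reader might take section 4.11 to name chest tightness as an HS risk. It does not, and section 9 names tightness only for sputum induction. Nor are overnight symptoms wholly ignored: continued wheezing is a suspension criterion, and failing such a criterion is an adverse event.

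The reply does not cover cases 2 and 3 above. A general query may elicit tightness, but nothing prompts for it, and an answer has no scale to go on. The reply also leaves the difference between 4.1 and 6.2 on wheeze untouched.

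**Conclusion.** The point holds in a limited form. The questionnaire lacks an item for chest tightness and one for patient-reported wheeze. The resulting gap is isolated tightness, plus overnight tightness or wheeze that resolves before a follow-up visit with no scheduled examination. Separately, sections 4.1 and 6.2 disagree on whether wheezing is intolerance.

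The documents do not support a claim that the intolerance proportion is materially biased. They give no rate for tightness or wheeze without shortness of breath, FEV1 fall or desaturation, so only the direction (towards fewer intolerant subjects) and the weight of a single case (3.6 points of 28, or 4.8 of an assumed 21) can be stated. This rests on the item list being the complete form, as section 5.3 presents it. The change is worth making because it is cheap and serves a stated objective, not because a large error has been shown.

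**What to change.** Add chest tightness and wheeze to the form, each on the existing 0-3 scale, wherever the questionnaire is given. The procedures table marks it at all seven visits, although section 4.7 does not list it for Visit 7. Include both items in the overnight query at Visits 2, 4 and 6. Report them as separate safety items and keep the eight-item total as it is, so that its cut-off keeps its meaning.

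Section 5.3 acts on any symptom at certain scores, and 4.1 and 4.11 act on any severe symptom. New items would therefore alter deferral, assessment and exclusion by default. The amendment should say explicitly whether those rules apply to the two items, and whether the score-of-3 limb in 6.2 counts them. The clinical part of that decision belongs to the study physicians. If the new items are kept out of 6.2, the intolerance proportion will not change, but the symptoms will at least be recorded and reported.

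Reconcile section 4.1 with section 6.2 on audible wheezing, so that one definition of intolerance governs the reported proportion.

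The cost is two lines on a form, the matching database fields and a minor amendment. Subjects already enrolled will lack the two items, so these should be reported with the number of subjects actually asked as the denominator.
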